General statistical Methods: A clinical response to apremilast for the purposes of this study will be defined as an Investigator Global Assessment score of 0 (clear) or 1 (almost clear). The end points of the study will be assessed at Week 16. A period of 16 weeks was chosen, as this was the time frame utilized for primary endpoint reporting in the ESTEEM clinical program.^{6,8} An additional 8 weeks of study drug will be provided to assess enhanced clinical benefit with continued use at 24 weeks. A rate of incompletion and/or drop out of subjects has been factored in to assure great than 16 patients will complete the study.

The analysis will be primarily descriptive. Mean, standard deviation, median, minimum, maximum, and 95% confidence interval for mean will be provided for continuous variables. Changes and percent changes from pre-treatment to on-treatment time points will be calculated for continuous efficacy points. Graphical displays of changes over time may be presented for key outcomes. Counts, percentages, and 95% confidence intervals will be provided for categorical variables. Subgroup analyses, such as gender stratification and stratification based on baseline treatment regimens, will be performed to identify a patient population that achieves the most benefit.

Efficacy analyses will only use data from participants who complete at least 16 weeks of study treatment in order to evaluate the primary endpoint.

Efficacy:

Primary Endpoint

Patients' Investigator's Global Assessment $(IGA)^9$ will be assessed at weeks 2, 4, 8, 16, and 24, with the primary endpoint being the proportion of patients with an IGA of 0 (clear) or 1 (almost clear) at Week 16.

Secondary Endpoints

Secondary endpoints will be assessed according to the scale of the outcome variable of interest. BSA and Eczema Area and Severity Index¹⁰ will be assessed along with IGA at all study visits. For quality of life outcomes, the Dermatology Life Quality Index (DLQI)¹¹ will be used to assess changes from baseline in overall score will be provided. Assessment of outcomes of each protocol-scheduled time point (Weeks 2, 4, 8, 16, and 24) will be performed for each endpoint. Various schemes will be assessed for missing data imputation if needed. The change in the patient's Numerical Rating Scale for Pruritus (NRS) will be assessed.¹²

Background and demographic characteristics:

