Subjects' age, weight, height and other continuous demographic and baseline characteristics will be summarized using descriptive statistics (mean, standard deviation, minimum and maximum), while gender, race and other categorical variables will be summarized with frequency tabulations. Medical history data will be summarized using frequency tabulations. Individual subject listings will be provided. A table of baseline demographic information of subjects who received study medication and controls will be provided for comparison between the two groups.

Safety:

Safety Primary Endpoints

The safety analysis will be descriptive in nature. All subjects who take at least 1 dose of the study medication will be included in the safety analyses. Safety and tolerability will be evaluated by tabulations of adverse events, which will be recorded from the time the subject signs informed consent. Adverse events will be classified on the basis of Common Terminology Criteria for Adverse Events (CTACAE) coding and summarized for each treatment. Adverse events will be summarized by system organ class, preferred term, relationship to study drug, and severity. Serious AEs and AEs leading to death or resulting in premature discontinuation will be tabulated and listed separately. Study medication-related AEs will be listed separately. Drop-out rate and reasons for early termination will be reviewed and tabulated.

Prior and concomitant medications will be reviewed and tabulated by treatment. Physical examination changes and vital signs including weight will be assessed for potential clinical significance; changes from pre-treatment to on-treatment time points will be tabulated for continuous parameters; as warranted.

Assessment of flare of atopic dermatitis will be summarized descriptively.

C. Subject Characteristics

Inclusion criteria:

- 1. Signed and dated informed consent indicating the subject has been informed of all aspects of the study
 - D. Non-English speakers may be enrolled in the study in accordance with the IRB's short form policy.

- 2. Subject is willing and able to comply with treatment plan, study drug administration, and study protocol requirements
- 3. Male or females of any ethnic origin or race at least 18 years of age at time of informed consent
- 4. Subject has a documented clinical diagnosis of chronic atopic dermatitis for at least 6 months prior to screening visit and is a candidate for systemic therapy

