Prior/Concomitant Medications

Subjects may take any medication that is not restricted by the protocol and would not be expected to interfere with the conduct of the study. As the purpose of this study is to evaluate the efficacy of apremilast 30 mg BID when combined with dupilumab, subjects must continue on a stable dose of dupilumab while also receiving the study drug.

All medications (prescription and non-prescription), treatments and therapies taken from screening through the last dose of study medication, including those initiated prior to the start of the study, must be recorded on the appropriate page of the subject documents. Record the dose, route of administration, indication, and the start and end date (when the medication was taken).

Permitted Concomitant Therapy:

The subject is required to continue on a concomitant stable dose of dupilumab treatment regimen throughout the study, given that they have been using the treatment for the minimum amount of time deemed necessary by the investigator to have experienced an inadequate clinical response. Once informed consent has been signed, subjects may not have additional atopic dermatitis medications prescribed outside of their existing atopic dermatitis treatment regimen listed at screening.

The following commonly used products are acceptable for use throughout the study: acetaminophen, loratadine, pseudoephedrine, guaifenesin, and calcium. Subjects must check with study personnel before initiating use of prescribed or over-the-counter medications during the study.

A nonmedicated emollient, i.e., Eucerin® cream (supplied by the study doctor), will also be allowed during the study; use must be stable throughout the study

Any patient found to have cellulitis on physical exam during the study will be treated with appropriate antibiotics. It is at the investigator's discretion whether the study drug will be continued or held.

Prohibited Concomitant Therapy:

- Use of any investigational medication
- Concomitant therapy with CYP450 enzyme inducers (e.g., rifampin, phenobarbital, carbamazepine, phenytoin), which may cause loss of efficacy of apremilast
- All atopic dermatitis therapies outside of the subject's existing treatment regimen at screening are prohibited

Treatment Compliance:

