Study personnel will review the instructions printed on the package insert with subjects prior to dispensing the study medication. New study medication will be dispensed according to the Schedule of Assessments. The subject will be instructed to return the study medication packaging, including any unused medication, to the study site at each visit for assessment of compliance. Subjects will be asked whether they have taken their medication as instructed at each study visit. Any problems with compliance will be reviewed with the subject.

Compliance will be assessed in two ways. Subjects will be responsible for returning unused study drug to the site. Pills will be counted to determine compliance. Subjects will also be responsible for recording the date and time they take the study drug in a medication diary. Compliance is defined as taking between 75%-125% of dispensed study medication.

Dupilumab injections will also be recorded in the medication diary.

Withdrawal/Termination criteria:

The following are considered sufficient reasons for discontinuing a subject from study drug:

- Adverse events that the investigator believes may cause severe or permanent harm or which rule out continuation of study drug
- Lack of therapeutic effect:
 - Subjects who experience a significant flare of atopic dermatitis, as defined by a sudden intensification of eczema, or as a diagnosis of erythrodermic atopic dermatitis may be discontinued from treatment and enter the observational follow- up phase of the study.
 - In addition, if the subject, in his or her opinion, feels that their disease is worsening or not responding to treatment, they may withdraw consent to participate.
- Subject withdraws consent
- Subject lost to follow-up
- Death
- Protocol violation

The reason for discontinuation will be recorded in the subject's medical records.

D. Risk/benefit assessment:

- 1. **Physical risk**: Physical risk includes potential side effects or unknown adverse events related to study medication. It is unknown how the combination of apremilast with dupilumab will affect subjects. Side effects may be worse or intensified on this combination. Subjects may be at a slightly higher risk of infection than those taking the drugs individually, but this is unknown. It is unknown if this combination will improve atopic dermatitis. AD could stay the same or get worse.

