PROTOCOL

Study Title:	Apremilast 30 mg BID combined with Dupilumab for the Treatment of Recalcitrant Moderate-to-Severe Atopic Dermatitis
Study Drug:	Oral Apremilast 30 mg BID
Sponsor :	[name] Tufts Medical Center Department of Dermatology [name] [contact] [contact] E-mail: [contact]
NCT:	NCT04306965

Version and Date:

Version June 2, 2021

Statistical Methods

Sample size: We will screen up to 20 patients to ensure that 16 patients complete the study.

General statistical Methods: A clinical response to apremilast for the purposes of this study will be defined as an Investigator Global Assessment score of 0 (clear) or 1 (almost clear). The end points of the study will be assessed at Week 16. A period of 16 weeks was chosen, as this was the time frame utilized for primary endpoint reporting in the ESTEEM clinical program.^{6,8} An additional 8 weeks of study drug will be provided to assess enhanced clinical benefit with continued use at 24 weeks. A rate of incompletion and/or drop out of subjects has been factored in to assure great than 16 patients will complete the study.

The analysis will be primarily descriptive. Mean, standard deviation, median, minimum, maximum, and 95% confidence interval for mean will be provided for continuous variables. Changes and percent changes from pre-treatment to on-treatment time points will be calculated for continuous efficacy points. Graphical displays of changes over time may be presented for key outcomes. Counts, percentages, and 95% confidence intervals will be provided for categorical variables. Subgroup analyses, such as gender stratification and stratification based on baseline treatment regimens, will be performed to identify a patient population that achieves the most benefit.

Efficacy analyses will only use data from participants who complete at least 16 weeks of study treatment in order to evaluate the primary endpoint.

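### The primary endpoint credits apremilast with a Week 16 clearance whatever other therapy preceded it, and drops subjects stopped early for flare

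*Protocol*

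**What the plan says.** Section II.B of the protocol, General statistical Methods, reads: "A clinical response to apremilast for the purposes of this study will be defined as an Investigator Global Assessment score" of 0 or 1. The primary endpoint is the proportion meeting this at Week 16. No condition is placed on other treatment received. The SAP repeats the definition and, like the protocol, fixes the analysis set: "Efficacy analyses will only use data from participants who complete at least 16 weeks of study treatment in order to evaluate the primary endpoint".

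The rest of the relevant text governs conduct and reporting:

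- **Prohibited Concomitant Therapy:** atopic dermatitis therapies outside the subject's "existing treatment regimen at screening are prohibited".
- **Prior/Concomitant Medications:** for every medication taken, "Record the dose, route of administration, indication, and the start and end date".
- **Withdrawal/Termination criteria:** the list, which includes protocol violation, opens with "The following are considered sufficient reasons for discontinuing a subject from study drug". Under lack of therapeutic effect, a subject with a significant flare "may be discontinued from treatment and enter the observational" follow-up phase.
- **Safety (section II.B):** "Prior and concomitant medications will be reviewed and tabulated by treatment", and "Assessment of flare of atopic dermatitis will be summarized descriptively". Neither is linked to the primary endpoint.

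**The concern.** The subjects respond inadequately to dupilumab and are candidates for systemic therapy. The protocol foresees flares severe enough to stop study drug, and its Alternatives item (section G) names prednisone and immunosuppressants as oral eczema medications. A systemic course during the study is therefore plausible, although one given for atopic dermatitis would breach the protocol.

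If it happens, the same clinical event can be counted in two ways, both favourable to apremilast. A subject kept on study drug who is clear at Week 16 is recorded as responding to apremilast, although the other drug may have done the work. A subject stopped before Week 16 is not recorded as a failure but removed. Which of the two applies depends on a discretionary decision by an unblinded investigator. No control arm offsets either effect, and this proportion is the study's primary result.

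**Working it through.** **Inputs.** Planned completers: 16, from up to 20 screened (Sample size, both documents). IGA visits: Weeks 2, 4, 8, 16 and 24. The documents give no target rate, test, threshold or frequency of on-study systemic treatment, so there is no planned figure to reproduce. The response counts below are assumptions.

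**Step 1: what the text does with each case.**

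| Subject | Counted as |
|---|---|
| Treated course, kept on drug, IGA 0/1 at Week 16 | Responder |
| Treated course, kept on drug, IGA 2 or more at Week 16 | Non-responder |
| Stopped before Week 16 for flare or such treatment | Not in numerator or denominator |

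Only the first and third rows are a problem. The second is already counted as failure.

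**Step 2: size of the first row.** Recounting one such responder as a non-responder lowers the rate by 1/N:

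- N = 12: 8.3 points
- N = 16: 6.25 points
- N = 20: 5.0 points

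This is an upper limit per subject. It applies only if the course, and not apremilast, produced the clearance.

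**Step 3: the rows side by side.** Assume 16 treated subjects, one affected, and r responders among the other 15, all of whom complete.

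| r | Kept and clear, (r+1)/16 | Stopped early, r/15 | Non-responder, r/16 |
|---|---|---|---|
| 1 | 12.5% | 6.7% | 6.25% |
| 3 | 25.0% | 20.0% | 18.75% |
| 7 | 50.0% | 46.7% | 43.75% |

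- Kept minus non-responder: (r+1)/16 − r/16 = 1/16 = 6.25 points at every r.
- Stopped minus non-responder: r/15 − r/16 = r/240, which is 0.4, 1.25 and 2.9 points for r = 1, 3 and 7.

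**Step 4: against the precision of the estimate.** Exact (Clopper-Pearson) 95% intervals: 4/16, 7.3% to 52.4%; 3/15, 4.3% to 48.1%; 3/16, 4.0% to 45.6%. The interval for 4/16 is 52.4 − 7.3 = 45.1 points wide, so a shift of 6.25 points lies well inside it.

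**Step 5: can the data sort out a case afterwards?** Not always. For a course given in Weeks 12 to 16, the last earlier scheduled IGA is Week 8, which is 16 − 8 = 8 weeks before the primary visit. The schedule cannot show whether the subject was already clear when the course began. The Week 24 IGA, taken on continued apremilast, can show whether clearance lasted. That is relevant but not conclusive.

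**The case against.** **The plan does have a rule.** A reader might infer that the plan is silent on how such an IGA counts, so that the decision would be made once the result is known. The documents do not support that. The responder definition and the completer set together determine the count: the observed IGA, regardless of other therapy. This can be defended as a treatment-policy reading. What stands against it is that the plan calls the result a response to apremilast, in a study with no control arm.

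**Conduct controls make the case uncommon.** New atopic dermatitis therapies are barred. Inclusion criterion 8 requires a stable concomitant regimen. Subjects must consult study staff before starting any medication, and drugs expected to interfere with the study are not permitted. Protocol violation is a listed reason to stop study drug. This largely stands: the kept-and-clear case needs a deviation or a tolerated exception, continuation on apremilast, and clearance. The controls do not change how such a subject is counted, and stopping study drug makes the third row of the table more likely.

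**Little depends on it.** The analysis is descriptive, the interval is wide, and at one site with about 16 subjects a case would be visible. This stands, and it limits the importance of the point.

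**Missing-data imputation could cover it.** It does not. That sentence sits under Secondary Endpoints and names no method, and an IGA observed after a steroid course is not missing.

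**Every systemic course should be failure.** A reader might also infer that a course for an unrelated illness must count as non-response. The documents give no basis for that, or for any particular window. Exclusion criterion 11 sets a washout before entry, not an analysis rule. Failing a subject stopped for an unrelated steroid, while dropping one stopped for flare without a drug, would make the denominator less consistent.

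**Conclusion.** The point holds in a limited form. As written, clearance after a systemic corticosteroid or immunosuppressant course is credited to apremilast in a subject kept on study drug, and a subject stopped early for flare or such treatment drops out of the rate. Both push the primary proportion upward. This sits poorly with the protocol's own filing of significant flare under lack of therapeutic effect.

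The size is at most 6.25 points per kept-and-clear subject with 16 completers. It is r/240 per early stop, about 0.4 to 2.9 points, under the assumption of 16 treated subjects with one affected and 1 to 7 responders among the rest. How many such subjects to expect cannot be derived from the documents. Larger shifts need several cases among 16, for which there is no support. No test or success threshold exists for the shift to cross, so only the reported rate and its interval are affected. This is a cheap improvement and does not undermine the design.

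**What to change.** Add to the SAP and to protocol section II.B, directly after the completer-only sentence:

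> In the primary analysis, a subject who starts or increases a systemic corticosteroid, systemic immunosuppressant or other prohibited atopic dermatitis therapy for atopic dermatitis before the Week 16 IGA is a non-responder. A subject whose study drug is stopped before Week 16 for flare, lack of effect or such therapy stays in the denominator as a non-responder, as an exception to the completer-only rule. A sensitivity analysis uses the observed Week 16 IGA where available. Systemic courses for other indications are listed with dates and IGA by visit, with a sensitivity analysis counting those close to Week 16 as non-response.

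The sponsor should put a number on how close to Week 16 counts before the data are seen. Any length is a choice.

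**Cost.** Four sentences. No new data are needed, because medication dose, indication and dates, and the reason for discontinuation, are already recorded. The reported rate may be slightly lower, including for a subject who was already clear before the course. For a course in Weeks 12 to 16, neither the sensitivity analysis nor the listing can settle that.

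**Limits.** Subjects stopped for adverse events alone still leave the denominator, so this does not replace a wider review of the completer-only set. A change in dupilumab frequency, or heavier use of an existing topical, would need its own sentence if the sponsor wants it covered.

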 - v. Mean and percentage change from baseline in Eczema Area and Severity Index (EASI) score at week 16

Safety Endpoints:

Safety and tolerability will be evaluated according to the frequency and severity of adverse events and changes in physical examinations or vital signs.

II. Research Plan

A. Overall Study Design:

Open label phase 2 investigational study of efficacy and safety of apremilast 30 mg BID in chronic atopic dermatitis when added to the FDA approved treatment dupilumab for atopic dermatitis that is not providing adequate clinical responses. The study will have 1 phase:

• Open label treatment period apremilast 30 mg BID

Following informed consent, subjects will be screened on the basis of atopic dermatitis severity and inadequate treatment response to current therapies. IGA, BSA, pruritus NRS, EASI, complete physical examination, medical history, and concomitant medications will be reviewed. Eligible subjects will be administered treatment with apremilast 30 mg BID while continuing their prior inadequate atopic dermatitis treatment regimen. During the treatment phase, study drug will be provided in an oral form and will be titrated over 5 days and then taken twice daily thereafter. Subjects return to clinic for reevaluation. Efficacy endpoints will be assessed at weeks 2, 4, 8, 16, and 24. Week 16 is the last week of study drug dispensation. Efficacy and safety indices will be assessed as per the Schedule of Assessments.

Treatment Assignment and Randomization

No randomization will be used, as this is an open label study. There will be no blinding and investigators will have knowledge of the treatment each subject is administered.

All patients seen in the Tufts Dermatology Clinic during the enrollment period who are not currently responding to existing FDA approved atopic dermatitis therapy and thus have not achieved a IGA of 0 or 1 at screening, and meet all other inclusion/exclusion criteria, will be offered participation in the study.

B. Statistical methods:

Sample size: We will screen up to 20 patients to ensure that 16 patients complete the study.

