1. **Study Procedures**: At the initial visit, a Investigator's Global Assessment (IGA) of disease will be performed to determine if the patient meets the inclusion criteria. A score on the NRS Pruritus

scale will be determined. A thorough medical history and a review of prior/concomitant medications will be taken at the screening visit. A complete physical examination including weight and vital signs (temperature, blood pressure) will also be performed. At the following visits according to the Schedule of Assessments, a IGA, BSA, DLQI survey, vital signs, NRS pruritus scale, EASI, a complete or targeted physical exam and review of concomitant medications and adverse events will be performed. Additionally, drug dispensing and accountability will also occur at all visits after the screening visit according to the Schedule of Assessments.

- Lab monitoring is not standard of care for patients using apremilast in clinic settings for the treatment of psoriatic disorders. Patients with psoriasis are frequently prescribed apremilast in addition to psoriasis biologic injectables, and it is not standard of care to perform lab tests for these patients that is outside of what is recommended for monitoring the safety of their injectable biologic alone. Atopic dermatitis patients taking apremilast are not at any increased risk compared to psoriasis patients taking apremilast. Dupilumab is a biologic, but this specific biologic does not require lab monitoring. For these reasons, lab monitoring will not be performed during this study as it would cause research subjects to undergo unnecessary testing. However, for all patients taking apremilast, it is standard of care to monitor weight at treatment visits and to ask patients about adverse symptoms. Both of these will be performed during the study based on the schedule of assessments.
- 2. **Subject Timeline**: 24 week duration of study treatment.

F. Assessment of Subject Safety and Development of a Data and Safety Monitoring Plan

- AE data will be collected at each study visit by asking the subject about their symptoms. The PI will review all AE data as they are collected, and the PI will sign off on AEs during the study visit. The AEs for the subjects will be stored in the subject's study documents and updated at each study visit. AEs will be collected from the time of ICF signature through the end of the study at all study visits.

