drug, or within 30 days of the subject's last dose of study drug, are considered immediately reportable events. Study drug is to be discontinued immediately and the subject instructed to return any unused portion of the study drug to the investigator(s). The pregnancy, suspected pregnancy, or positive pregnancy test must be reported to Amgen Safety immediately facsimile using the Pregnancy Report form provided by Amgen. An authorization form to request the collection of this information from the pregnant partner of a male subject will be submitted to the IRB for review and approval prior to the collection of this information. The study team will request that subject approach their pregnant partner to obtain authorization, and the pregnant partner may contact the study team for more information.

G. Subject Participation

- 1. **Recruitment**: Recruitment will occur through the outpatient dermatology clinic at Tufts Medical Center once IRB approval is obtained. Goals for recruitment in terms of screening treatment regimens include: 16 subjects completing the study. Up to 20 may be screened to allow for screen fails.
 - Dermatologists in the TMC department of dermatology will be informed about the ongoing trial and its key inclusion/exclusion criteria. Dermatologists can inform their patients about the study during the patient's regular scheduled clinic visit. If a patient is interested, research staff will come down to the dermatology clinic to inform the patient further. If the subject chooses to proceed with a screening visit, this will be conducted in a private research room where informed consent will be obtained. Alternatively, the screening visit can be scheduled for a future date. Dermatologists may also tell their patients about this study and provide research staff contact information to the patient
 - The clinical recruitment website will provide online information about the study. Additionally, this trial will be listed on clinicaltrials.gov. Study team contact information will be provided in both of these websites, and interested subjects may call the department for more information. There are no other recruitment materials.
 - These two methods have been effective in the past for our recruitment of other investigator-initiated trials of similar sample sizes.
- 2. Registration: Not applicable.

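### Does the sample-size statement need correcting because it asks for 16 completers in one place, more than 16 in another, and gives no loss rate?

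*Protocol*

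**What the plan says.** The Sample size paragraph of the protocol's Statistical methods (Research Plan, section B), repeated in the SAP, reads: "We will screen up to 20 patients to ensure that 16 patients complete the study". The Recruitment item (section G.1) gives the same numbers and a reason for the margin: "16 subjects completing the study. Up to 20 may be screened to allow for screen fails".

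The General statistical methods paragraph, in both documents, says that losses after entry were allowed for and states the yield differently. In the protocol this is "A rate of incompletion and/or drop out of subjects has been factored in to assure great than 16 patients will complete the study", and the SAP repeats it: "factored in to assure great than 16 patients will complete the study". Neither document gives a rate for screen failure, dropout or the two combined.

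Two time points could define completion. The efficacy set is stated outright: "Efficacy analyses will only use data from participants who complete at least 16 weeks of study treatment". The Subject Timeline (section E.2) gives a "24 week duration of study treatment", and the Payment item's maximum of $300 at $50 per visit is 300/50 = 6 visits, the sixth being Week 24 in the Schedule of Assessments.

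**The concern.** This is the only sample-size statement in the trial, and efficacy is analysed in completers only, so the completer count is the denominator of the primary endpoint. Four things look wrong:

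- There are two targets, 16 and at least 17, close together in the same SAP.
- The margin above the target is explained by screen failures in one place and by dropout in another. The cap is on subjects screened, so both losses must come out of it.
- The reader cannot tell whether completion means Week 16 or Week 24.
- The plan speaks of ensuring or assuring a yield without stating the loss rate that would support it.

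If these points had consequences, the trial could end smaller than intended, and nobody could say afterwards whether it had reached its planned size.

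**Working it through.** **Inputs from the documents.** Cap: 20 screened (Sample size; Recruitment). Target: 16 (Sample size; Recruitment) or at least 17 (General statistical methods, read literally). Loss rates: none stated. Significance level, power and effect size: none, because the analysis is described as primarily descriptive.

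**Step 1: the plan's own figure.** The 20 cannot be derived forward without a loss rate, so solve backwards.

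- Target 16: 20 − 16 = 4 spare places; implied combined loss 1 − 16/20 = 20%; check 16/(1 − 0.20) = 20.
- Target 17: 20 − 17 = 3 spare places; implied combined loss 1 − 17/20 = 15%; check 17/(1 − 0.15) = 20.

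Either target is compatible with 20. No sum in the documents is wrong.

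**Step 2: chance of reaching the target.** Assume independent patients, with completers X ~ Binomial(20, p) and p = (1 − screen failure)(1 − dropout). All loss rates below are assumptions, shown as a range.

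| Screen failure / dropout | p | Expected completers (20p) | P(X ≥ 16) | P(X ≥ 17) |
|---|---|---|---|---|
| 5% / 5% | 0.9025 | 18.1 | 0.96 | 0.88 |
| 5% / 10% | 0.855 | 17.1 | 0.85 | 0.67 |
| 10% / 10% | 0.81 | 16.2 | 0.67 | 0.46 |
| 15% / 15% | 0.7225 | 14.5 | 0.31 | 0.15 |
| 20% / 20% | 0.64 | 12.8 | 0.10 | 0.04 |

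Solving for the combined loss at which the chance of reaching the target equals a given level:

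| Chance of reaching target | Loss, target 16 | Loss, target 17 |
|---|---|---|
| 95% | 10.4% | 7.1% |
| 90% | 12.7% | 9.0% |
| 50% | 23.0% | 18.0% |

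A guarantee in the strict sense therefore needs low loss. Missing 16 becomes more likely than not only above about 23% combined loss. The documents place the trial at no particular point in this range.

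**Step 3: cost of a shortfall.** Exact (Clopper-Pearson) 95% limits for x responders out of n are the 0.025 quantile of Beta(x, n − x + 1) and the 0.975 quantile of Beta(x + 1, n − x). The responder counts are illustrative.

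| Responders / completers | 95% CI | Half-width |
|---|---|---|
| 5/16 | 11.0% to 58.7% | 23.8 points |
| 4/13 | 9.1% to 61.4% | 26.2 points |
| 8/16 | 24.7% to 75.3% | 25.3 points |
| 6/13 | 19.2% to 74.9% | 27.8 points |

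Losing three completers costs 26.2 − 23.8 = 2.4 points or 27.8 − 25.3 = 2.5 points of half-width. The interval is wide either way, and its interpretation does not change.

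**Step 4: are the statements incompatible?** A yield above 16 also satisfies a target of 16, so the two differ in ambition by one patient. The Recruitment item does not say that the margin is for screen failures only, and the dropout sentence mentions neither 20 nor the spare places. Both can be true of one margin. The definition of completion does not affect the analysis, because the efficacy set has its own rule of at least 16 weeks of treatment.

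**The case for a change.** The strongest case for a change is that the facts are not in dispute and the correction would be cheap. The two targets are both there, the shared margin is real, and no loss rate is stated. If all four spare places went to screen failures, 16 would start treatment, a single dropout would miss 16, and exceeding 16 would be impossible. Even at the 20% combined loss that 16/20 implies, the chance of at least 16 is only 0.63. One consistent sentence would add no patients and no visits.

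All of that stands as a comment on drafting. It does not show that the design misses its stated size. The loss rates that produce a likely shortfall are assumed, and a 95% assurance standard appears nowhere in the documents. Ensuring a number of completers is ordinary planning language in a small, single-centre, open-label study. The literal reading as 17 rests on a phrase with a visible grammatical slip, probably meant as at least 16, while the Sample size and Recruitment statements agree on 16. Inserting rates or responder counts chosen by an outside reader would give the sponsor's text a precision that has no source.

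**Conclusion.** No change to the plan is called for. This is a one-patient clerical slip together with an unstated planning assumption; it is not an arithmetic error. Resolving it would alter no estimate, interval or conclusion:

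- The analysis is descriptive, and no hypothesis test or decision rule uses 16 or 17.
- The primary-endpoint denominator will be whoever meets the stated 16-week rule, whatever target was written down.
- Safety covers everyone who takes at least one dose, so the completer count does not affect it.
- The Safety section commits to tabulating the dropout rate and the reasons for early termination, so a shortfall would be reported.

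A plausible bad case, 13 completers instead of 16, costs about 2 to 3 points of half-width on an interval already about 24 to 25 points either side. That figure rests on illustrative responder counts, and the probabilities in the working rest on assumed loss rates and independence between patients. An analyst can take 16 as the target, treat the cap of 20 as covering both kinds of loss, and report the numbers screened, treated, and completing Week 16 and Week 24. Whether restricting efficacy to completers is sound is a separate question and does not depend on this one.
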